## 14.8 Appendix 8 Protocol Amendment History

The Protocol Amendment Summary of Changes Table for the current amendment is located directly before the Table of Contents. A summary of previous amendments is provided below.

Amendment	Date	Main reason(s)
1	17 September 2018	Various clarifications on eligibility and discontinuation criteria, and corrections of mistakes.
2	1 March 2019	
 
• Addition of the option to dispense 50 µg tablets only.
 
• Addition of the systematic collection of signs and symptoms of right heart failure and events of disease progression.
 
• Correction of mistakes.
 

3	6 May 2019	
 
• Dispersion of tablets in water was prohibited. Only patients able to swallow tablets whole with water can be enrolled.
 

4	18 March 2020	
 
• Additional treatment administration option with soft food.
 
• Sample size increase in Cohort 3.
 

COVID-19 Appendix Version 1	16 June 2020	To provide a guidance on study conduct during the COVID-19 pandemic
5	05 October 2020	To reflect updates in safety reporting process.
6	19 May 2021	The main reason for the amendment was to add alternative options for administration of study intervention and implement other minor corrections.
COVID-19 Appendix Version 2	19 May 2021	To implement updates about 'Study conduct related to COVID-19 vaccine deployment for non-COVID-19 clinical trials' per Medicines and Healthcare products Regulatory Agency (MHRA) vaccination guidance.

Confidential

## **COVID-19 APPENDIX**

### **GUIDANCE ON STUDY CONDUCT DURING THE COVID-19 PANDEMIC**

It is recognized that the Coronavirus Disease 2019 (COVID-19) pandemic may have an impact on the conduct of this clinical study due to, for example, self-isolation/quarantine by participants and study-site personnel; travel restrictions/limited access to public places, including hospitals; study site personnel being reassigned to critical tasks.

In alignment with recent health authority guidance, the sponsor is providing options for study related participant management in the event of disruption to the conduct of the study. This guidance does not supersede any local or government requirements or the clinical judgement of the investigator to protect the health and well-being of participants and site staff. If, at any time, a participant's safety is considered to be at risk, study intervention will be discontinued, and study follow-up will be conducted.

Scheduled visits that cannot be conducted in person at the study site will be performed to the extent possible remotely/virtually or delayed until such time that on-site visits can be resumed. At each contact, participants will be interviewed to collect safety data. Key efficacy endpoint assessments should be performed if required and as feasible. Participants will also be questioned regarding general health status to fulfill any physical examination requirement.

Every effort should be made to adhere to protocol-specified assessments for participants on study intervention, including follow up. Modifications to protocol-required assessments may be permitted via COVID-19 Appendix after consultation with the participant, investigator, and the sponsor. Missed assessments/visits will be captured in the clinical trial management system for protocol deviations. Discontinuations of study interventions and withdrawal from the study should be documented with the prefix "COVID-19-related" in the case report form (CRF).

The sponsor will continue to monitor the conduct and progress of the clinical study, and any changes will be communicated to the sites and to the health authorities according to local guidance. If a participant has tested positive for COVID-19, the investigator should contact the sponsor's responsible medical officer to discuss plans for study intervention and follow-up. Modifications made to the study conduct as a result of the COVID-19 pandemic should be summarized in the clinical study report.

### **GUIDANCE SPECIFIC TO THIS PROTOCOL**

In relation to Protocol Section 4.3 (Inclusion criterion #7), urine pregnancy tests for females of childbearing potential may be shipped from the site to the subjects' home, in case a re-supply via site-visit is not possible.

In relation to Protocol Section 5.1.6 (Study treatment supply), for subjects unable to visit the clinic/hospital, direct-to-patient (DTP) shipment of study drugs may be implemented, where allowed per local regulations and if requested by the treating study physician. Where DTP

shipments are deemed necessary, the process should be coordinated between the site and sponsor staff following the “COVID-19 DTP Guidance Document”.

In relation to Protocol Section 12.3 “Informed Consent”, consenting and re-consenting of subjects will be performed as applicable for the measures taken (including remote consenting by phone or video consultation) and according to local guidance for informed consent as applicable.

## **STUDY CONDUCT RELATED TO COVID-19 VACCINE DEPLOYMENT FOR NONCOVID-19 CLINICAL TRIALS**

- Study participants can undergo a COVID-19 vaccination procedure in compliance with applicable local governmental regulations.
- No pharmacokinetic interaction between the study intervention and currently available COVID-19 vaccines are expected. In addition, based on the mechanism of action of the study intervention and COVID-19 vaccines, no relevant interaction is expected.
- Any COVID-19 vaccine administered to a study participant is considered a concomitant medication and should be reported on the electronic case report form (eCRF).
- For serious adverse events (SAEs) reported after COVID-19 vaccination, the investigator should provide narrative details on the SAE form to allow adequate assessment of causality relationship between the reported SAE and vaccination. This is particularly relevant in cases where the reported SAE is an expected event with the study intervention and the COVID-19 vaccine. If the event is serious and considered to be related to both the COVID-19 vaccine and the study intervention, it is a serious adverse reaction and expectedness must be assessed. Suspected unexpected serious adverse reaction (SUSAR) reporting will be performed if the serious adverse reaction is unexpected as per applicable reference safety document.

8.1. Appendix 1 List of Abbreviations.....	28
8.2. Appendix 2 Definitions of Adverse Events of Special Interest.....	29

LIST OF IN-TEXT TABLES AND FIGURES

Table 1: SAP Version History Summary 4
Table 2: Study Analysis Set Usage 8
Table 3: Study periods definition..... 8

VERSION HISTORY**Table 1: SAP Version History Summary**

SAP Version	Approval Date	Change	Rationale
Original SAP	10 June 2020	Not Applicable	Initial release
Amendment 1	11 August 2020	See rationale	
 1) Add outputs for COVID-19 related AEs. 2) Add more analysis for concomitant PAH-specific medications 3) Update AESI definitions and provide more details on AESI definitions as an appendix of SAP to align with selexipag program level AESI definitions: ie. Remove thrombocytopenia from anaemia AESI definition, add PVOD AESI and medication error and pregnancy. 4) Add definitions for persistent and recurrent AESIs and average annualized event rates
Amendment 2	02 May 2022	See rationale	
 1) Update the SAP based on Protocol Version 8, Amendment 7 to add optional PK Interim Analysis 3. 2) Add Week 16 CSR deliverable, including all participants having Week 16 assessment. 3) Remove the persistent TEAE definition as the team agree that no separate output is need for it

1. INTRODUCTION

The purpose of this study is to confirm the selexipag doses in children from ≥ 2 to < 18 years of age with PAH that led to an exposure similar to that in adult participants. The selection of the selexipag starting dose was based on a PK extrapolation from adults to pediatric participants. In addition, the safety and tolerability of selexipag in children from ≥ 2 to < 18 years of age are assessed.

This statistical analysis plan (SAP) contains definitions of analysis sets, derived variables, and statistical methods for the analysis of safety and exploratory efficacy and other endpoints.

The analyses of pharmacokinetic (PK) data, as well as PK and PK/PD modeling are not included in this document but described in separate analysis plans.

1.1. Study Objectives

Primary:

- The primary objective of the study is to confirm the selexipag starting dose(s), selected based on pharmacokinetic (PK) extrapolation from adults, which leads to similar exposures as adult doses in children from ≥ 2 to < 18 years of age with pulmonary arterial hypertension (PAH) by investigating the PK of selexipag and its active metabolite ACT-333679 in this population.

Secondary:

- To evaluate the safety and tolerability of selexipag in children from ≥ 2 to < 18 years of age with PAH.

Exploratory:

- To explore the relationship between drug exposure at the individual maximum tolerated dose (iMTD) and 6-minute walk distance (6MWD) at each time point of assessment.
- To explore the relationship between drug exposure and N-terminal pro b-type natriuretic peptide (NT pro-BNP) at each time point of assessment.
- To explore the relationship between drug exposure and Echocardiography (Echo) variables at each time point of assessment.
- To explore the time to disease progression/clinical worsening from first study drug dose up to EOT + 7 days.

Other:

- To assess palatability of selexipag formulation at each time point of assessment using a 5-point facial hedonic scale.
- To assess acceptability of selexipag formulation at each time point of assessment using a 3-point categorical scale.

1.2. Study Design

This is a prospective, multi-center, open-label, single-arm, Phase 2 study. Approximately 60 participants will be enrolled in 3 different age cohorts (based on age at baseline/enrollment/Visit 2) to obtain at least 45 participants with evaluable PK profiles:

- Cohort 1: ≥ 12 to < 18 years of age (approximately 20 enrolled participants to obtain at least 15 participants with evaluable PK profiles)

- Cohort 2: ≥ 6 to < 12 years of age (approximately 20 enrolled participants to obtain at least 15 participants with evaluable PK profiles)
- Cohort 3: ≥ 2 to < 6 years of age (approximately 20 enrolled participants to obtain at least 15 participants with evaluable PK profiles).

The starting dose is based on the body weight category of the participants, using the data from the population PK model in the GRIPHON/AC-065A302 study targeting the exposure observed in adult PAH participants at a starting dose of 200 μg , taken orally, twice a day. The continuous relationship between dose and body weight is used to define body weight categories and starting dose for each body weight category such that – on average – the exposure ($\text{AUC}_{\tau, \text{ss}, \text{combined}}$) will be comparable to that of a 70 kg adult but not exceeding the exposure of a 50 kg adult.

Dosing scheme (by body weight) is defined as follows:

- 100 μg starting dose for participants with a body weight from ≥ 9 to < 25 kg
- 150 μg starting dose for participants with a body weight from ≥ 25 to < 50 kg
- 200 μg starting dose for participants with a body weight ≥ 50 kg

Selexipag is to be dosed twice daily (bid) and during the up-titration period of 12 weeks, it is recommended that the doses are increased weekly in increments equal to the starting dose until the participants reach their individual maximum tolerated dose (iMTD), or until the maximum dose corresponding to 8-fold that of the starting dose (based on their baseline weight category) is achieved.

The starting dose selection will be confirmed or adjusted after completion of each age cohort by updating the population PK model (interim and final PK analysis).

Enrollment started with both Cohort 1 and Cohort 2 (participants ≥ 12 to < 18 years, and ≥ 6 to < 12 years of age, respectively). After completion of PK assessments in at least 15 participants in Cohort 1 at Week 12, the dose-exposure relationship was established using a population PK model (interim analysis 1). Enrollment of Cohort 3 (children ≥ 2 to < 6 years of age) was started once the appropriate doses were confirmed by modelling and simulation in a second interim analysis of PK data from the children older than 6 years (i.e., Cohorts 1 and 2) and the confirmation that there was no safety concern based on IDMC reviews.

The PK data pooled from all 3 age cohorts will be modelled to allow dosing recommendations for all children ≥ 2 years of age. A final PK analysis will be prepared based on the overall PK and safety data up to Week 16 evaluation. The selection of the dosing regimen for the Phase 3 study will be based on the safety, tolerability, and PK results evaluated in the interim or final PK analysis (as applicable).

Participants who discontinue the treatment any time before the profile PK sampling day will be replaced within the age cohort.

Study Periods

The study consists of the following consecutive periods:

Screening period: Lasts up to 42 days; starts with the signature of the informed consent and ends with the administration of the first study treatment dose.

Treatment period: Starts from the first dose of study treatment at Baseline/enrollment visit and ends on the day of the last dose of selexipag (End of Treatment [EOT]). This includes:

- **Up-titration period:**

From the first dose of study treatment until the participant reaches individual maximum tolerated dose (iMTD). This period is estimated to last up to 12 weeks.

- **Maintenance period:**

After Week 12: the participants will continue study treatment at the same dose up to Week 16.

After Week 16: study treatment will continue as long as it remains beneficial for the participant up to maximum of 5 years after last (Cohort 3) participant first visit.

EOT visit: this visit should be conducted within 1 week of the last dose of study treatment.

Safety Follow-up period: Starts on the day after the last dose of study treatment and ends about 30 days thereafter with a phone call that indicates the End of Study (EOS).

2. ANALYSIS DETAILS

2.1. Analysis Sets

- **Screened Analysis Set:** Screened analysis set includes all participants who are screened and have a participant identification number.
- **Full Analysis Set:** Full analysis set includes all enrolled participants who were eligible to receive the study drug.
- **Safety Analysis Set:** Safety analysis set includes all participants included in Full Analysis Set who receive at least one dose of the study drug. Since all enrolled participants received at least one dose of study drug, the Full Analysis Set and Safety Analysis Set are the same in this study. For simplicity, the Safety Analysis Set will be used for all safety and efficacy analyses.
- **Pharmacokinetic Analysis Set (PKS):** PK analysis set comprises all participants included in the Safety Analysis Set who complied with the protocol sufficiently and did not deviate from the protocol in a way that might affect the PK outcome of the study. Criteria for sufficient compliance include exposure to treatment, availability of PK measurements, and absence of major protocol deviations that have an impact on the PK. Further details are provided in the PK and modeling analysis plan.

For all analyses, except the time to disease progression event, only the scheduled visits data will be used in summary outputs; both the scheduled and unscheduled visits data will be included in the listings.

The analysis set usage is summarized as following:

Table 2: Study Analysis Set Usage

	Screened Analysis Set	Full Analysis Set	Safety Analysis Set	PK Analysis Set	PK
Participant disposition	X	X	X		
Participant information (medical history, concomitant medication, contraceptives)			X		
Participant information (demographics, baseline characteristics, baseline disease characteristics)			X		
Treatment exposure, treatment discontinuation, drug accountability and compliance, protocol deviation			X		
Safety analyses			X		
Other endpoints analyses			X		
PK analyses				X	X
Efficacy exploratory analyses			X		
Sensitivity Analysis, for Efficacy exploratory analyses			X		
All listings for disposition/Recruitment	X	X	X		
All listings for Participant information	X	X	X		
All other Listings			X		

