	
All analyses of safety variables will be carried out descriptively using the Safety Analysis Set, consisting of all treated participants, and will be performed as follows:
 
 
• in the overall population.
 
• by iMTD dose groups.
 
• by age cohort.
 
 
The number and percentage of participants with at least one TEAE / TESAE / AE leading to study treatment discontinuation will be described by system organ class (SOC) and preferred term (PT) up to EOT + 3 days, and separately for the up-titration period (until Week 12) and the maintenance phase (> Week 12 until EOT + 3 days).
 
The same analysis will be performed according to the maximum intensity of reported AEs and their relationship to the study drug.
 
The number and percentage of treatment-emergent deaths will be described by SOC and PT up to EOT + 3 days.
 
For each laboratory and ECG variable, the number and percentage of participants with at least one treatment-emergent marked abnormality will be summarized up to EOT + 3 days.
 
Vital signs and sexual maturation variables will be summarized over time up to EOT + 3 days, using descriptive statistics for continuous variables.

STUDY COMMITTEES
	
An IDMC has the overall responsibility for safeguarding the interests of participants by monitoring safety data obtained in the study and by making appropriate recommendations based on the reported data, thus ensuring that the study is being conducted with the highest scientific and ethical standards. The PK results of the interim analyses (after completion by Cohorts 1 and 2, and final PK results of all three cohorts) will be provided to the IDMC for review, if requested by the committee. The IDMC will be fully operational prior to enrollment of the first participant into the study. The

	composition and operation of the IDMC is described in the IDMC charter.
--	---

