#### **10.1.2 Full Analysis Set**

The Full Analysis Set (FAS) includes all enrolled participants who were eligible to receive the study drug.

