#### **10.1.4 Safety Analysis Set**

The Safety Analysis Set includes all participants who received at least one dose of study treatment.

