4. SAFETY ANALYSIS

Safety and tolerability will be assessed throughout the study, from signing of the Informed Consent Form (ICF) until the participant's last study-related activity. The study will include the following evaluations of safety and tolerability: adverse events, clinical laboratory tests (including TSH, thyroid antibodies, T3, T4, pregnancy tests, Plasma NT pro-BNP), ECG, vital signs, growth (weight, height and BMI), sexual maturation (Tanner Stage), childbearing potential and physical examinations.

Unless otherwise specified, all safety analyses will be carried out descriptively (using the Safety Analysis Set) in the overall population, by age cohort and body weight group.

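### The SAP ties the Safety Analysis Set to an eligibility-conditioned Full Analysis Set, whereas the protocol counts every dosed child; the SAP should return to the protocol's definition

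*SAP*

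**What the plan says.** Protocol 10.1.4 sets one condition: "The Safety Analysis Set includes all participants who received at least one dose of study treatment". The synopsis agrees and describes the "Safety Analysis Set, consisting of all treated participants".

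SAP 2.1 sets two: "Safety analysis set includes all participants included in Full Analysis Set who receive at least one dose of the study drug". The set it nests in is defined just before: "Full analysis set includes all enrolled participants who were eligible to receive the study drug". Protocol 10.1.2 gives the Full Analysis Set the same eligibility wording, but the protocol does not make the Safety Analysis Set a subset of it.

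The SAP then adds: "Since all enrolled participants received at least one dose of study drug, the Full Analysis Set and Safety Analysis Set are the same". On that ground it uses the Safety Analysis Set for efficacy as well as safety, whereas protocol 10.1.5 assigns the exploratory efficacy variables to the Full Analysis Set. SAP section 4 confirms the safety use: unless otherwise specified, "all safety analyses will be carried out descriptively (using the Safety Analysis Set) in the overall population".

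In both documents the PK Analysis Set is drawn from the Safety Analysis Set.

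**The concern.** A safety population normally needs only exposure to the drug. The SAP adds a condition on eligibility, which is a property of the child and not of exposure, and leaves the term undefined. If it means that every inclusion and exclusion criterion was truly met, a child dosed in error is in the protocol's safety population and outside the SAP's.

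This can happen under the protocol. Section 7.2.4.1 lets a site verify eligibility on a local laboratory sample when central results are late, and a central value arriving afterwards could contradict it on, for example, the hemoglobin or creatinine exclusions in section 4.4.

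Safety and tolerability are the secondary objective. Children dosed outside the criteria cannot be assumed to carry the same adverse-event risk as the rest, so leaving them out could bias the descriptive rates. Under the same reading they would also be missing from the protocol-deviation output, where the error ought to be visible.

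**Working it through.** The plan gives no figure to reproduce. The check compares definitions, with simple arithmetic for scale.

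**1. The two sets side by side**

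- Protocol 10.1.4: Safety = {dosed}.
- SAP 2.1: Safety = {enrolled and eligible and dosed}.
- Difference: {dosed and (not enrolled or not eligible)}.

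If only enrolled children are dosed, the difference reduces to {enrolled, dosed, not eligible}. It is empty if eligible means cleared and enrolled. It can be non-empty if eligible means that every criterion was met.

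**2. Whether the SAP's equality statement closes the gap**

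The reason given is that every enrolled participant was dosed. That removes {enrolled and not dosed}, so within the Full Analysis Set dosing takes nobody out and the two SAP sets are indeed equal. It says nothing about who was admitted to the Full Analysis Set. Suppose 60 children are enrolled and dosed and one is later found ineligible. Under the strict reading the Full Analysis Set has 59 members and the Safety Analysis Set has the same 59. The equality holds, and the protocol's set still has 60.

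**3. What SAP 3.2 implies about intent**

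SAP 3.2 reports the number of dosed participants as a percentage of the Full Analysis Set, counting as dosed anyone with a record in the treatment log. In the same example the strict reading gives 60/59 = 101.7%. A percentage above 100 is not a sensible design, so this denominator points to a Full Analysis Set of all enrolled participants.

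**4. Which outputs are affected under the literal reading (SAP Table 2)**

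- Safety Analysis Set only: safety analyses, exposure, treatment discontinuation, accountability and compliance, protocol deviations, demographics and medical-history summaries, exploratory efficacy and its sensitivity analyses, other endpoints, and all remaining listings.
- Also on the Screened and Full sets: participant disposition, and the listings for disposition, recruitment and participant information.

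The affected child would therefore still appear in some outputs, through the Screened Analysis Set, but not in the adverse-event tables.

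**5. Scale**

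With the planned enrollment of about 60, and about 20 per cohort, one child is 1/60 = 1.7% of the total and 1/20 = 5% of a cohort.

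Neither document gives a rate of dosing outside the criteria. Assuming a rate p, independent between children, the chance of at least one such child among 60 is 1 − (1 − p)^60:

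| Assumed p | Chance of at least one |
|---|---|
| 1% | 1 − 0.99^60 = 45% |
| 2% | 1 − 0.98^60 = 70% |
| 5% | 1 − 0.95^60 = 95% |

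These are illustrations under assumed rates, not estimates for this trial. They give the chance that such a child exists. They become a chance of losing the child from the tables only under the strict reading.

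**The case against.** The best defense is that eligible means no more than cleared for treatment. Protocol 5.1.3 has the investigator confirm the criteria and then enroll the child through the IRT, which assigns the bottles. A child who passes that step could fairly be called eligible to receive study drug, whatever emerges later. Nothing in either document removes a participant from the Full or Safety Analysis Set after an eligibility deviation. The SAP 3.2 denominator fits this reading. So does the disposition scheme, which has no category for enrolled children left out of the Full Analysis Set, and so does reporting protocol deviations on the Safety Analysis Set. Protocol 4.3 and 4.4 forbid waivers, and the SAP version history records no intention to narrow the safety population.

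Most of this stands as evidence of intent. It does not remove the mismatch. SAP 3.2 already defines screening failures as screened children who were not enrolled, so if the eligibility condition adds nothing beyond enrollment it is redundant, and if it adds something it contradicts the protocol. A ban on waivers does not prevent errors.

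Three stronger inferences are tempting and are not supported:

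- That SAP 3.2 expects dosed ineligible children because it lists unmet inclusion and met exclusion criteria. That listing is on the Screened Analysis Set, beside the reasons for not enrolling, and screening failures are enough to explain it.
- That every table is affected. Disposition and several listings also use wider sets.
- That PK data would certainly be lost. The nesting implies it on a literal reading, but the SAP leaves PK analyses and the detailed PK set criteria to separate plans that are not available here.

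**Conclusion.** The definitions differ on the page, and the SAP's equality statement does not reconcile them. Applied literally, the SAP rule would leave a dosed child later found not to meet a criterion out of the outputs run on the Safety Analysis Set and out of the PK Analysis Set.

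A reader might conclude that such children do drop out of all safety tables. The documents do not go that far. The consequence depends on a strict reading of an undefined word, the SAP's own denominators suggest that all enrolled children may have been meant, and neither document reports a child dosed while ineligible. If all enrolled was the intent and only enrolled children were dosed, correcting the text changes no result. Under the strict reading, each affected child costs 1.7% of the planned total or 5% of a cohort, and the direction of any bias in adverse-event rates cannot be derived from the documents.

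The correction is still warranted: a stated SAP rule contradicts the protocol on who belongs in the safety population.

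**What to change.** In SAP 2.1:

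- Replace the Safety Analysis Set definition with the protocol's sentence, "The Safety Analysis Set includes all participants who received at least one dose of study treatment", and delete the requirement of Full Analysis Set membership.
- In the Full Analysis Set definition, either delete the eligibility condition or define it as enrolled through the IRT. Make the same clarification in protocol 10.1.2 if the protocol is next amended.
- Keep exclusions based on deviations in the PK Analysis Set only, where the test is impact on PK, and check that the separate PK and modeling plan uses the same parent set.

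The cost is an edit to two definitions. No new data are needed. If programming already takes all dosed children, nothing needs rerunning; if it filters on eligibility, that filter comes out.
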